	7.2.2 Safety Analyses from Randomization through All of Follow-up	
0	7.2.3 Statistical Analysis of Adverse Events	
8	Interim Analyses	
	8.1 Interim Analyses for Early Stopping	18

1 Preface

This Statistical Analysis Plan (SAP) describes the planned analysis and reporting for Clinical Islet Transplantation protocol CIT-02, "Strategies to Improve Long Term Islet Graft Survival".

This phase 2 study focuses on treating islets pre-transplant and subjects (during and posttransplant) with Lisofylline (LSF), an agent with a unique spectrum of anti-inflammatory, anti-apoptotic and β cell enhancing properties, to improve β cell function and viability, maximizing pre-transplant functional islet mass, islet engraftment and long-term function in subjects with type 1 diabetes.

The structure and content of this SAP provides sufficient detail to meet the requirements identified by the FDA and International Conference on Harmonisation of Technical Requirements for Registration of Pharmaceuticals for Human Use (ICH): Guidance on Statistical Principles in Clinical Trials [1]. All work planned and reported for this SAP will follow internationally accepted guidelines, published by the American Statistical Association [2] and the Royal Statistical Society [3] for statistical practice.

The following documents were reviewed in preparation of this SAP:

- Clinical Research Protocol CIT-02.
- Case report forms (CRFs) for Protocol CIT-02.
- ICH Guidance on Statistical Principles for Clinical Trials.

The reader of this SAP is encouraged to also read the clinical protocol for details on the conduct of this study, the operational aspects of clinical assessments, and timing for completing assessments for a subject in this study.

Exploratory analyses not necessarily identified in this SAP may be performed to support the clinical development program. Any post-hoc, or unplanned, analyses not identified in this SAP that are performed will be clearly identified in the applicable clinical study report.

2 Study Design and Objectives

2.1 Study Design

This is a multi-center, single arm, open-label trial assessing the experimental treatment regimen as well as determining the proportion of subjects with insulin independence.

A larger phase 3 trial (Protocol CIT-07) in which subjects are treated with the standard islet transplant immunosuppression regimen is being conducted in parallel with Protocol CIT-02. Eligible subjects will be randomized to receive immunosuppression under either Protocol CIT-07 or this study (Protocol CIT-02) at the time a suitable islet preparation is available for transplantation. The randomization will provide a mechanism for balance between the two studies and to help ensure an objective selection of subjects.

2.2 Study Objectives

2.2.1 Primary Objective

The primary objective of this study is to estimate the proportion of subjects who are insulin independent at 75 ± 5 days following the first islet cell infusion among subjects treated with LSF.

2.2.2 Secondary Objectives

The secondary objectives of this study are to:

- 1. Increase the proportion of patients rendered insulin independent with a single (1donor) islet transplant at 1 year by preservation of β -cell mass and enhancement of β -cell function.
- 2. Enhance the magnitude of glucose and non-glucose stimulated insulin responses of islet allografts.
- 3. Achieve long-term insulin independence by preventing the decline in β -cell function.

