2.3 Study Endpoints

2.3.1 Primary Endpoint

The primary endpoint for the study is the proportion of insulin-independent subjects at day 75 ± 5 days following the first islet transplant.

The primary aim of the analysis is to estimate the true rate of this outcome in subjects analyzed by the intention-to-treat (ITT) principle. If the primary endpoint cannot be evaluated for an individual because of death, withdrawal of consent, or another reason, a failure (i.e. not insulin independent) will be imputed. However, if there is an evaluation done at a time longer than 75 days after transplant and before an additional islet transplant (a second or third transplant), the later evaluation will be used. All imputations of the primary endpoint will be reported with the primary analysis.

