2.3.2.2 Additional Efficacy Endpoints

The following is a comprehensive list of the additional efficacy endpoints. In general, these efficacy endpoints are summarized for baseline (the most recent value prior to transplant), at 75 days and 365 days following the initial islet transplant, and again at 75 days, 365 days, and 730 days following the final islet transplant. Any variables that deviate from this schedule, as indicated by the schedule of events in the protocol, will be summarized accordingly. Imputations are not performed for missing values in the additional efficacy endpoints.

- Proportion of insulin-independent subjects
- Percent reduction in insulin requirements
- HbA1c
- Mean amplitude of glycemic excursions (MAGE)
- Glycemic lability index (LI)
- Ryan hypoglycemia severity (HYPO) score
- Clarke Score
- Basal (fasting) and 90-min glucose and c-peptide derived from the mixed-meal tolerance test (MMTT)
- C-peptide: (glucose X creatinine) ratio
- β-score
- Acute insulin response to glucose (AIR_{glu}), insulin sensitivity, and disposition index (DI) derived from the insulin-modified frequently-sampled IV glucose tolerance (FSIGT) test
- Glucose variability and hypoglycemia duration derived from the continuous glucose monitoring system® (CGMS)
- Quality of life (QOL) measures
- The proportion of subjects receiving a second islet transplant

- The proportion of subjects receiving a third islet transplant
- The number of severe hypoglycemic events

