3.1 Study Period

The study period of this trial is a 24-month follow-up visit after the final islet transplant. Subjects may undergo up to 3 transplants in the course of this study; the final transplant must occur not later than 8 months following the first transplant.

In the first period, individuals who meet the general inclusion criteria will be approached regarding participation in the study. After informed consent has been obtained, they will be formally enrolled into the study. Eligibility will be confirmed based on the results of the screening visit procedures detailed in the study Schedule of Events (Appendix 1 of the CIT-02 protocol). Enrolled subjects who meet the eligibility screening for the studies will be put on the waiting list for an islet transplant.

Once a compatible islet preparation becomes available, a subject's eligibility will be reconfirmed, and eligible subjects who are randomized to Protocol CIT-02 will begin immunosuppression therapy on Day 0 (Day 0 is defined as the day of transplant).

During the post-transplant follow-up period, subjects may receive up to two additional transplants. After receiving his/her initial islet transplant, if a subject does not meet the criteria for insulin independence described in the Study Definitions section of the CIT-02 protocol, but has either a basal or stimulated C-peptide level ≥ 0.3 ng/mL (0.1 nmol/L), s/he will be considered for a second islet transplant. A second islet transplant will be

considered after day 85, but before 8 months after the first islet transplant and when all required metabolic assessments are complete. If, after the second islet transplant, both basal and stimulated C-peptide levels remain <0.3 ng/mL (0.1 nmol/L), the recipient will be considered to have failed the endpoint, and immunosuppression will be managed as described in the protocol. A third islet transplant will be considered only if all the criteria described in Section 7.6.2 of the CIT-02 protocol are met. Islet transplant recipients who have completed 8 months of follow up after their first infusion will no longer be eligible for additional islet transplants under the CIT-02 protocol. The number of excluded subjects and the number of protocol violations will be noted throughout the duration of the study.

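### Secondary Objective 1 asks for 1-year insulin independence on a single-donor transplant, but no listed endpoint or analysis in the SAP estimates it

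*SAP*

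**What the plan says.** - **Objective.** SAP 2.2.2, item 1, concerns subjects "rendered insulin independent with a single (1donor) islet transplant at 1 year".
- **Endpoint.** SAP 2.3.2.2, which presents its list of additional efficacy endpoints as comprehensive, has "Proportion of insulin-independent subjects" with no condition on the number of transplants. It is summarised "at 75 days and 365 days following the initial islet transplant". A second set of time points is counted from the last graft: "again at 75 days, 365 days, and 730 days following the final islet transplant". Section 6.2.1 repeats the schedule and assigns categorical endpoints to template AT2: a proportion with an exact 95% interval at each time point.
- **Re-transplantation.** Under 3.1 a subject becomes a candidate for a second transplant "if a subject does not meet the criteria for insulin independence described in the Study Definitions section" and has sufficient C-peptide. The second transplant is "considered after day 85, but before 8 months after the first islet transplant", and "the final transplant must occur not later than 8 months following the first transplant".
- **Contrast with the primary endpoint.** In 2.3.1, when the Day 75 evaluation is missing, a later one may stand in only if it was done "before an additional islet transplant (a second or third transplant), the later evaluation will be used". Section 6.1 has the same condition.
- **Related items.** Section 2.3.2.2 lists the proportions receiving a second and a third transplant as separate endpoints. It also rules out imputation for the additional efficacy endpoints.

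**The concern.** The objective contains a condition (one donor, one transplant) that the endpoint lacks. The condition matters at 1 year because the whole re-transplant window has closed by then. Candidates for re-transplantation are subjects whose first graft did not make them insulin independent. If such a subject is insulin independent at Day 365 after the first transplant, that is a success of the transplant sequence and not of the single graft.

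The SAP protects the primary endpoint from a later graft, yet has no rule at Day 365, where a later graft can actually be present. The statistician would have to choose among three handlings: status at the visit, exclusion, or failure. In an open-label trial of 12 subjects that choice could be made with the outcomes in view. Section 4.2 lets further derived variables be created and documented in programs without amending the SAP. At stake is whether a stated objective gets a prespecified estimate, and whether the nearest available figure is mistaken for it.

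**Working it through.** **Timing.** Eight months is 8 × 365/12 ≈ 243 days. The window for additional transplants therefore runs from Day 86 to about Day 243 after the first. At Day 365 after the first transplant, a second graft is between 365 − 243 = 122 and 365 − 86 = 279 days old. Every permitted re-transplant precedes that visit, and none precedes Day 75 ± 5.

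**The two planned 1-year time points.**
- Day 365 after the first transplant includes subjects with one, two or three grafts.
- Day 365 after the final transplant coincides with the first for single-graft subjects. For the others it is 1 year after a second or third graft, so it is not a single-donor rate either.

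**Interval method.** Exact binomial (Clopper-Pearson), N = 12. The lower bound solves Pr(X ≥ r) = 0.025 and the upper bound solves Pr(X ≤ r) = 0.025. (This is the standard pairing; 6.1 prints the two sums against the opposite bounds.) For r = 6 it gives 0.2109 to 0.7891, which reproduces the 0.21 to 0.79 in Table 1 of 2.4.

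**Illustration.** N = 12 comes from 2.4. The SAP gives no re-transplant rate and no success rate after re-transplantation, so the remaining counts are assumptions. Let s = 3 be insulin independent at Day 365 on one graft, k = 4 re-transplanted, and m = 3 of those 4 insulin independent at Day 365.

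| Handling of re-transplanted subjects | Formula | Result |
|---|---|---|
| Scored as failure | s/N | 3/12 = 25% (0.05 to 0.57) |
| Status at the visit | (s + m)/N | 6/12 = 50% (0.21 to 0.79) |
| Excluded | s/(N − k) | 3/8 = 37.5% |

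Only the first row answers Objective 1.

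**Range over m, with s = 3.** Status at the visit exceeds the single-donor rate by m/12:
- m = 0: 25%, no difference
- m = 1: 4/12 = 33% (0.10 to 0.65)
- m = 3: 6/12 = 50% (0.21 to 0.79)
- m = 6 (needs at least 6 re-transplanted): 9/12 = 75% (0.43 to 0.945)

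Each affected subject adds 1/12 = 8.3 points. With a common denominator the difference cannot be negative.

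**Can the listed endpoints recover the single-donor rate?** Suppose the report shows 6/12 insulin independent and 4/12 re-transplanted. Between 0 and 4 of the re-transplanted could be among the 6, so the single-graft successes lie anywhere from 6 − 4 = 2 to 6, that is 17% to 50%. The two separate proportions do not fix their overlap.

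**The case against.** The strongest reply is that the unqualified Day 365 proportion is a coherent summary in its own right. The SAP never labels it a single-donor rate or ties it to Objective 1. The numbers of second and third transplants are reported too, so readers will see that re-transplantation occurred. Section 6.2 calls the secondary analyses descriptive and not a basis for an efficacy decision, and 4.2 leaves room for the missing variable. The protocol, not shown, holds the definition of insulin independence and the visit schedule.

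Much of this stands. It limits the severity and rules out four stronger readings that a reader might infer:

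- *That the SAP counts re-transplanted subjects as successes.* It does not say so; it is silent. Even on the most literal reading, only those insulin independent at Day 365 would count.
- *That Day 365 after the first transplant is the only 1-year analysis.* Day 365 after the final transplant is also planned, although it does not isolate single-donor results.
- *That a second-graft success could carry the trial to the 50% mark in 8.1.* That mark and the historical 15–20% belong to the Day 75 endpoint, which precedes any re-transplant.
- *That key secondary endpoint 1 has the same defect.* It concerns HbA1c and severe hypoglycemia, and nothing in 2.3.2.1 claims that it is single-donor.

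The reply does not remove the core. The list is presented as comprehensive and has no entry for Objective 1. The overlap calculation shows that the separate re-transplant proportions cannot supply it. Permission to derive a variable later is not prespecification.

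**Conclusion.** The point holds as a gap between objective and endpoint: the SAP states a single-donor, 1-year objective and plans no analysis that estimates it. The nearest figure, classified by status at Day 365 after the first transplant, equals the single-donor rate only if no re-transplanted subject is insulin independent then. Otherwise it is higher by 8.3 points per such subject, assuming all 12 subjects are in the denominator. Excluding re-transplanted subjects can also overstate the rate.

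An upward bias of a known size is not established. It depends on how many subjects are re-transplanted, how many of them succeed and which handling is chosen, and the SAP gives none of these. The 25% against 50% comparison rests wholly on assumed counts. Severity is moderate: the estimate is secondary and descriptive, and no sample size, stopping rule or primary analysis depends on it.

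**What to change.** Add one endpoint to 2.3.2.2 and 6.2.1: insulin independent at Day 365 after the first transplant, with no additional islet transplant before that evaluation. Score re-transplanted, dead, withdrawn or unevaluable subjects as failures, use the ITT denominator, and report an exact two-sided 95% interval. State that this endpoint is an exception to the no-imputation rule for additional efficacy endpoints. Tie it to Objective 1 by name.

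Keep the existing Day 365 proportion and label it as regardless of the number of transplants. Breaking down key secondary endpoint 1 and the continuous endpoints by number of transplants is optional.

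The cost is a short wording change and one variable derived from transplant dates. No treatment, visit or sample size changes. The figure reported for Objective 1 may be lower than the unqualified proportion.

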2.3 Study Endpoints

2.3.1 Primary Endpoint

The primary endpoint for the study is the proportion of insulin-independent subjects at day 75 ± 5 days following the first islet transplant.

The primary aim of the analysis is to estimate the true rate of this outcome in subjects analyzed by the intention-to-treat (ITT) principle. If the primary endpoint cannot be evaluated for an individual because of death, withdrawal of consent, or another reason, a failure (i.e. not insulin independent) will be imputed. However, if there is an evaluation done at a time longer than 75 days after transplant and before an additional islet transplant (a second or third transplant), the later evaluation will be used. All imputations of the primary endpoint will be reported with the primary analysis.

2.3.2 Secondary Endpoints

Because there is a large number of secondary endpoints, it is impractical to account for all multiple comparisons. Unadjusted p-values will be reported which allow others to apply any multiple comparison or false discovery rate approach they deem necessary to the p-values resulting from this study.

2.3.2.1 Key Secondary Endpoints

There are two key secondary endpoints in this study. If a key secondary endpoint for a subject is not evaluable, a failure will be imputed. All imputations will be reported with the key secondary endpoint analyses.

- 1. The proportion of subjects with an HbA1c level < 7.0% and free of severe hypoglycemic events from Day 28 to Day 365, inclusive, after the first islet transplant.
- 2. The proportion of subjects with an HbA1c level < 7.0% and free of severe hypoglycemic events from Day 28 to Day 365, inclusive, after the last islet transplant.

2.3.2.2 Additional Efficacy Endpoints

The following is a comprehensive list of the additional efficacy endpoints. In general, these efficacy endpoints are summarized for baseline (the most recent value prior to transplant), at 75 days and 365 days following the initial islet transplant, and again at 75 days, 365 days, and 730 days following the final islet transplant. Any variables that deviate from this schedule, as indicated by the schedule of events in the protocol, will be summarized accordingly. Imputations are not performed for missing values in the additional efficacy endpoints.

- Proportion of insulin-independent subjects
- Percent reduction in insulin requirements
- HbA1c
- Mean amplitude of glycemic excursions (MAGE)
- Glycemic lability index (LI)
- Ryan hypoglycemia severity (HYPO) score
- Clarke Score
- Basal (fasting) and 90-min glucose and c-peptide derived from the mixed-meal tolerance test (MMTT)
- C-peptide: (glucose X creatinine) ratio
- β-score
- Acute insulin response to glucose (AIR_{glu}), insulin sensitivity, and disposition index (DI) derived from the insulin-modified frequently-sampled IV glucose tolerance (FSIGT) test
- Glucose variability and hypoglycemia duration derived from the continuous glucose monitoring system® (CGMS)
- Quality of life (QOL) measures
- The proportion of subjects receiving a second islet transplant

- The proportion of subjects receiving a third islet transplant
- The number of severe hypoglycemic events

2.3.2.3 Safety Endpoints

The following safety endpoints will be reported:

- Safety, including incidence of post-transplant infections, malignancies, morbidity, and other AEs (e.g., increased body weight and hypertension) associated with conventional immunosuppression.
- Renal function as measured by serum creatinine, GFR, and other relevant laboratory parameters.
- Lipid profiles (triglycerides, total cholesterol, LDL cholesterol, HDL cholesterol) over time.

For the time periods from randomization until 365 days following the initial transplant and then from randomization until the end of follow-up, the following safety endpoints are assessed:

- The incidence and severity of AEs related to the islet transplant procedure including: bleeding (> 2 g/dL decrease in Hb concentration); segmental portal vein thrombosis; biliary puncture; wound complication (infection or subsequent hernia); and increased transaminase levels (> 5 times upper limit of normal [ULN]) (NOTE: These are AEs that are generally thought to be related to the islet transplant procedure. Actual relatedness is only captured for SAEs.)
- The incidence and severity of AEs related to the immunosuppression including: allergy; reduction in GFR; increase in urinary albumin excretion; addition or intensification of anti-hypertensive therapy; addition or intensification of antihyperlipidemic therapy; oral ulcers; lower extremity edema; gastrointestinal toxicity; neutropenia, anemia, or thrombocytopenia; viral, bacterial, or fungal infections; and benign or malignant neoplasms (NOTE: These are AEs that are generally thought to be related to immunosuppression. Actual relatedness is only captured for SAEs.)
- The incidence of a change in the immunosuppression drug regimen
- The incidence of immune sensitization defined by presence of anti-HLA antibodies absent prior to transplantation.

At 365 ± 14 days after the first islet transplant the following endpoint is assessed:

• The incidence of worsening retinopathy as assessed by change in retinal photography from pre-transplant.

3.1 Study Period

The study period of this trial is a 24-month follow-up visit after the final islet transplant. Subjects may undergo up to 3 transplants in the course of this study; the final transplant must occur not later than 8 months following the first transplant.

In the first period, individuals who meet the general inclusion criteria will be approached regarding participation in the study. After informed consent has been obtained, they will be formally enrolled into the study. Eligibility will be confirmed based on the results of the screening visit procedures detailed in the study Schedule of Events (Appendix 1 of the CIT-02 protocol). Enrolled subjects who meet the eligibility screening for the studies will be put on the waiting list for an islet transplant.

Once a compatible islet preparation becomes available, a subject's eligibility will be reconfirmed, and eligible subjects who are randomized to Protocol CIT-02 will begin immunosuppression therapy on Day 0 (Day 0 is defined as the day of transplant).

During the post-transplant follow-up period, subjects may receive up to two additional transplants. After receiving his/her initial islet transplant, if a subject does not meet the criteria for insulin independence described in the Study Definitions section of the CIT-02 protocol, but has either a basal or stimulated C-peptide level ≥ 0.3 ng/mL (0.1 nmol/L), s/he will be considered for a second islet transplant. A second islet transplant will be

considered after day 85, but before 8 months after the first islet transplant and when all required metabolic assessments are complete. If, after the second islet transplant, both basal and stimulated C-peptide levels remain <0.3 ng/mL (0.1 nmol/L), the recipient will be considered to have failed the endpoint, and immunosuppression will be managed as described in the protocol. A third islet transplant will be considered only if all the criteria described in Section 7.6.2 of the CIT-02 protocol are met. Islet transplant recipients who have completed 8 months of follow up after their first infusion will no longer be eligible for additional islet transplants under the CIT-02 protocol. The number of excluded subjects and the number of protocol violations will be noted throughout the duration of the study.

